5.2 Criteria for Starting Subsequent Cycles

A cycle may be repeated every 28 days if the patient 1) has at least stable disease 2) all pre-cycle studies required per [Section 8.1](#) meet eligibility criteria-as defined in [Section 4.0](#) and 3) is otherwise eligible to continue agent administration per the requirements in [Section 6.0](#).

5.2.1 Recommendations for Starting Each Weekly 3-day Course:

BAY 1895344 (elimusertib) is administered on a 3-day on and 4-day off schedule, repeated 4 times each cycle. Hematologic toxicities are the most common toxicities with BAY 1895344 (elimusertib). Eligibility criteria require an ANC \geq 1000/ μ L and Platelets \geq 100,000/ μ L, hence these parameters also need to be met to start any cycle (See [section 4.1.11.1](#)). Once a cycle has started, patients are required to have an ANC $>$ 500/ μ L and Platelets $>$ 50,000/ μ L within 48 hours prior to initiation of each 3 day interval of BAY 1895344 (elimusertib) administration (i.e. ANC and platelet parameters must be met (without transfusion) within 48 hours of initiation of days 8, 15, and 21). If parameters are not met, this 3-day interval of BAY 1895344 (elimusertib) will be omitted and attempted to restart the following week (e.g. day 15 or 21). If more than one 3-day block of BAY 1895344 (elimusertib) is missed within a cycle (i.e. $<$ 75% of planned therapy is given for a particular cycle), that would be considered a hematologic DLT.

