5.5 Definition of Dose-Limiting Toxicity (DLT)

DLT will be defined as any of the following events that are possibly, probably or definitely attributable to protocol therapy. The DLT observation period for the purposes of study dose-escalation (Part A) will be the first cycle of therapy. Please refer to [Section 13.5.4](#) for AE resolution definitions

Dose limiting hematological and non-hematological toxicities are defined differently.

5.5.1 Non-Hematological Dose-Limiting Toxicity:**5.5.1.1 Any Grade 3 or greater non-hematological toxicity attributable to protocol therapy with the specific exclusion of:**

- Grade 3 nausea and vomiting of < 3 days duration
- Grade 3 liver enzyme elevation, including ALT/AST/GGT that returns to Grade \leq 1 within 7 days. See [Appendix IV](#) for Adverse Event grading for liver function grading parameters in children and adolescents.

Note: For the purposes of this study the ULN for ALT is defined as 45 U/L.

- Grade 3 hypophosphatemia, hypokalemia, hypocalcemia or hypomagnesemia responsive to supplementation
- Any Grade 2 non-hematological toxicity that persists for \geq 7 days and is considered sufficiently medically significant or sufficiently intolerable by patients that it requires treatment interruption.
- Note: Allergic reactions that necessitate discontinuation of study drug will not be considered a dose-limiting toxicity.

5.5.2 Hematological dose limiting toxicity:

- Grade 4 neutropenia (ANC $< 500/\mu\text{L}$) that persists for \geq 7 days despite holding BAY 1895344 (elimusertib) for 3 days
- Grade 4 thrombocytopenia (Platelet count $< 25,000/\mu\text{L}$)
- Grade 3 thrombocytopenia (Platelet count $< 50,000/\mu\text{L}$) that persists for \geq 7 days despite holding BAY 1895344 (elimusertib) for 3 days *OR* is associated with clinically significant bleeding
- Failure to meet hematological criteria to initiate weekly dosing ([Section 5.2.1](#)) or subsequent cycles of therapy ([Section 5.2](#)) by cycle day 42 (within 14 days of planned start of the subsequent cycle) will be considered dose limiting toxicity.
- Failure to receive at least 75% of the planned number of BAY 1895344 (elimusertib) doses during any cycle (i.e., 9 of 12 planned doses) due to delays attributable to myelosuppression would be considered a hematologic DLT.

5.5.2.1 Note: Grade 3 or 4 febrile neutropenia will not be considered a dose-limiting toxicity.

5.6: THERAPY DELIVERY MAPS (TDMS) FOR CYCLE 1

Page 1 of 1

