Therapy Delivery Map – Cycle 1

This Therapy Delivery Map (TDM) relates to Cycle 1. Cycle 1 lasts 28 days. Please record the dose level in the chart below. Treatment may continue in the absence of unacceptable toxicity. Use a copy of this page once for Cycle 1.

This form is to be completed and uploaded into RAVE at the end of every cycle.

Criteria to start this cycle are listed in [Section 5.2](#). Extensive details are in [Section 5.0](#) and [Section 9.0](#).

This TDM is on 2 pages.

DRUG	ROUTE	DOSAGE	DAYS	IMPORTANT NOTES
BAY 1895344 (elimusertib) IND# [REDACTED]	Oral (Tablet)	_____ mg/m ² /dose BID Dose level 1 max dose = 40 mg BID Dose level -1 max dose = 30 mg BID Part B patients \geq 18 years old: 40 mg BID	1-3 8-10 15-17 22-24	On days that BAY 1895344 (elimusertib) is due to be given, it should be administered twice daily preferably at the same time of day each day. Take BAY 1895344 (elimusertib) one (1) hour before or two (2) hours after a meal with plenty of water.

Assigned Dose Level Ht cm Wt kg BSA m² Age \geq 18 years yes. no

Date Due	Date Given	Day	BAY 1895344 (elimusertib) Nomogram Dose mg qAM. _____ mg qPM	Studies
Enter actual dose administered below				
		PRE	_____ mg _____ mg	a-e, f*, g-i, j^, k, m#, n%, q\$, r@
		1	_____ mg _____ mg	a, b, d, e, f*, g, h, l, o&, p!
		2	_____ mg _____ mg	
		3	_____ mg _____ mg	o&
		4		
		5		
		6		
		7		
		8	_____ mg _____ mg	e, f* 1
		9	_____ mg _____ mg	
		10	_____ mg _____ mg	o&, p!
		11		
		12		
		13		
		14		
		15	_____ mg _____ mg	e, f*, 1
		16	_____ mg _____ mg	
		17	_____ mg _____ mg	
		18		
		19		
		20		
		21		
		22	_____ mg _____ mg	e, f*, j^, 1
		23	_____ mg _____ mg	
		24	_____ mg _____ mg	
		25		
		26		
		27		
		28		

* Please refer to [Section 8.1](#) for the specific timing of these observations.

Observations in Cycle 1

- a. History
- b. Physical Exam
- c. Performance Status
- d. Height, Weight, BSA
- e. Vital Signs
- f. CBC, differential, platelets: *Once weekly. If patients develop Grade 4 neutropenia or Grade 3 or 4 thrombocytopenia, CBC/differential/platelets should be checked at least twice per week (every 3-4 days) until recovery to Grade 3 neutropenia or Grade 2 thrombocytopenia, or until the criteria for dose limiting toxicity are met. For patients who experience hematological dose limiting toxicity, CBCs should be checked at least weekly until recovery of ANC and platelet count to eligibility criteria
- g. SGPT (ALT), Albumin, Bilirubin

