This form is to be completed and uploaded into RAVE at the end of every cycle.

Criteria to start this cycle are listed in [Section 5.2](#). Extensive details are in [Section 5.0](#) and [Section 9.0](#).

This TDM is on 2 pages.

DRUG	ROUTE	DOSAGE	DAYS	IMPORTANT NOTES
BAY 1895344 (elimusertib) IND# [REDACTED]	Oral (Tablet)	mg/m ² /dose BID Dose level 1 max dose = 40 mg BID Dose level -1 max dose = 30 mg BID Part B patients ≥ 18 years old: 40 mg BID	1-3 8-10 15-17 22-24	On days that BAY 1895344 (elimusertib) is due to be given, it should be administered twice daily, preferably at the same time of day each day. Take BAY 1895344 (elimusertib) one (1) hour before or two (2) hours after a meal with plenty of water.

Assigned Dose Level Ht cm Wt kg BSA m² Age ≥ 18 years yes no

Date Due	Date Given	Day	BAY 1895344 (elimusertib) Nomogram Dose mg qAM. mg qPM	Studies
Enter actual dose administered below				
		1	mg mg	a-d, e*, f, g, i, j&
		2	mg mg	
		3	mg mg	
		4		
		5		
		6		
		7		
		8	mg mg	
		9	mg mg	
		10	mg mg	
		11		
		12		
		13		
		14		
		15	mg mg	e*
		16	mg mg	
		17	mg mg	
		18		
		19		
		20		
		21		
		22	mg mg	
		23	mg mg	
		24	mg mg	a-d, h^, j&, k!, l#
		25		
		26		
		27		
		28		

* Please refer to [Section 8.1](#) for the specific timing of these observations.

Cycle 2 +

Required Observations in Cycle 2 +

Page 2 or 2

- a. History
- b. Physical Exam
- c. Height, Weight, BSA
- d. Vital Signs
- e. CBC, differential, platelets: * **Must be obtained within 72 hours of the start of each cycle and on day 15 of all subsequent cycles.** If patients develops Grade 4 neutropenia or Grade 3 or 4 thrombocytopenia, CBC/differential/platelets should be checked at least twice weekly (every 3-4 days) until recovery to Grade 3 neutropenia, Grade 2 thrombocytopenia or until the criteria for dose limiting toxicity are met. For patients who experience hematological dose limiting toxicity, CBCs should be checked at least weekly until recovery of ANC and platelet count to eligibility criteria. Patients who have dose adjustment due to hematologic toxicity attributable to BAY 1895344 (elimusertib), are required to have CBCs once weekly to confirm the safety of this adjusted dose during the cycle. Please see [Section 6.1](#) for details.
- f. SGPT (ALT), Albumin, Bilirubin
- g. Electrolytes including serum creatinine, calcium (Ca⁺⁺), phosphorus (PO₄), magnesium (Mg⁺⁺)

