¹ If patients develop Grade 4 neutropenia or Grade 3 or 4 thrombocytopenia, CBC/differential/platelets should be checked twice per week (every 3 to 4 days) until recovery to Grade 3 neutropenia, Grade 2 thrombocytopenia, or until the criteria for dose limiting toxicity are met. For patients with hematological dose limiting toxicity, CBCs should be checked at least weekly until recovery to eligibility criteria. Please see [Section 5.2.1](#) for details.

THIS PROTOCOL IS FOR RESEARCH PURPOSES ONLY, SEE PAGE 1 FOR USAGE POLICY

- ² Women of childbearing potential require a negative pregnancy test prior to starting treatment; See [Section 4.2.1](#)
- ³ Tumor Disease Evaluation [^]should be obtained on the next consecutive cycle after initial documentation of either a PR or CR. Subsequent scans may restart 2 cycles after the confirmatory scan. Please note that for solid tumor patients, if the institutional investigator determines that the patient has progressed based on clinical or laboratory evidence, he/she may opt not to confirm this finding radiographically.
- ⁴ Tibial Radiographs should only be obtained in patients without epiphyseal closure at the time of enrollment, prior to start of therapy and if baseline tibial radiographs are open then another will be obtained after cycle 1, every 3 cycles thereafter and at the end of study treatment. The end of study treatment observation is not required, if already obtained within the final month of therapy. Reference [Section 8.7](#) for further instruction on monitoring for growth plate toxicity.
- ⁵ Tumor pathology and genomics report indicating a qualifying molecular aberration to enroll on study must be submitted via upload to MediData/RAVE. Details of genomic studies noted in [Section 4.1.3](#).

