- ⁶ Must be obtained within 72 hours of the start of each cycle and on day 15 of all subsequent cycles. If patients develop Grade 4 neutropenia or Grade 3 or 4 thrombocytopenia, CBC/differential/platelets should be checked at least twice weekly (every 3-4 days) until recovery to Grade 3 neutropenia, Grade 2 thrombocytopenia or until the criteria for dose limiting toxicity are met. For patients who experience hematological dose limiting toxicity, CBCs should be checked at least weekly until recovery of ANC and platelet count to eligibility criteria. Patients who have a dose adjustment due to hematologic toxicity attributable to BAY 1895344 (elimusertib), are required to have CBCs checked once weekly to confirm the safety of this adjusted dose during the cycle. Please see [Section 6.1](#) for details.
- ⁷ If greater than 7 days from pre study labs, please collect CBC, differential, platelets, bilirubin, albumin and serum creatinine within 48 hours prior to cycle 1, dose 1. These labs must still meet eligibility to receive dose 1 (as per [Section 4.0](#)).

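### From Cycle 2 onward, the count rule for each 3-day block (Section 5.2.1) has no scheduled CBC for the blocks on days 8 and 22

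*Combined protocol and SAP*

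**What the plan says.** - **The rule (Section 5.2.1).** Once a cycle is under way, ANC above 500/µL and platelets above 50,000/µL, without transfusion, must be shown "within 48 hours prior to initiation of each 3 day interval of BAY 1895344 (elimusertib) administration". The days are given as "within 48 hours of initiation of days 8, 15, and 21". If the limits are not met, the block is left out. Missing more than one block in a cycle counts as a hematologic DLT. The section does not limit any of this to Cycle 1.
- **Dosing days (Sections 5.6 and 5.7, delivery maps).** "1-3 8-10 15-17 22-24". The treatment plan in Section 5.1 agrees.
- **Routine counts, Cycle 1 (Section 5.6, item f).** "CBC, differential, platelets: *Once weekly". The map marks them on days 8, 15 and 22 as well as day 1.
- **Routine counts, Cycles 2+ (Section 5.7 item e; Section 8.1 footnote 6).** "Must be obtained within 72 hours of the start of each cycle and on day 15 of all subsequent cycles". The map marks the CBC on days 1 and 15 only.
- **Additional counts.** These are at least twice weekly after Grade 4 neutropenia or Grade 3 or 4 thrombocytopenia. After a hematologic DLT, "CBCs should be checked at least weekly until recovery to eligibility criteria" (Section 8.1 footnote 1). After a dose change, "Patients who have a dose adjustment due to hematologic toxicity attributable to BAY 1895344 (elimusertib), are required to have CBCs checked once weekly" (Section 8.1 footnote 6).
- **Consequences.** For escalation, "The DLT observation period for the purposes of study dose-escalation (Part A) will be the first cycle of therapy" (Section 5.5). The 75% dosing criterion in Section 5.5.2, however, covers any cycle, and Section 6.1.1 cites Section 5.2.1 among the sources that define dose-limiting cytopenia.

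**The concern.** A hold rule works only if its input is collected. From Cycle 2 onward the rule asks for a fresh count before three blocks, and the schedule supplies one for a single block. The additional counts do not fill the gap, because they begin only after a severe cytopenia, a DLT or a dose adjustment is already known. They cannot reveal a new cytopenia.

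Two things are at stake. The first is safety: a patient below the limits on day 8 or day 22 could be given the block because nobody looked. The protocol itself describes hematologic toxicity as the most common kind with this drug. The second is the data. Omitted blocks, the 75% criterion and the Section 6.1 reductions and removals all depend on these counts. If some sites draw them under Section 5.2.1 and others follow the schedule, hematologic events after Cycle 1 will be ascertained unevenly, and the toxicity summary will partly reflect site practice.

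The day label adds a smaller problem: a count timed to the day 21 named in Section 5.2.1 may be too old for a dose given on day 22.

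**Working it through.** The plan states no figure on this point, so the check sets the rule against the schedule.

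**Inputs.** Blocks start on days 1, 8, 15 and 22 (Section 5.1 and both maps). Routine CBCs in Cycles 2+ fall within 72 hours (3 days) of day 1, and on day 15 (Section 5.7 item e; Section 8.1 footnote 6). The permitted age of a count before a within-cycle block is 48 hours, or 2 days (Section 5.2.1). The maximum is 26 cycles (Section 5.1).

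**Age of the latest routine count at each within-cycle block, Cycles 2+**

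| Block start | Latest routine CBC | Age | Within 2 days? |
|---|---|---|---|
| Day 8 | Day 1, or up to 3 days earlier | 8 − 1 = 7 days, up to 7 + 3 = 10 days | No |
| Day 15 | Day 15 | 0 days | Yes |
| Day 22 | Day 15 | 22 − 15 = 7 days | No |

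So 2 of 3 within-cycle checks are uncovered in each cycle. Section 8.0 tolerates unavoidable departures of up to 72 hours, but this does not close the gap: even a draw made 3 days late would be 7 − 3 = 4 days old.

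**Accumulation for a patient who never triggers additional CBCs**

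- Through Cycle 2 (1 cycle): 2 of 3.
- Through Cycle 6 (5 cycles): 5 × 2 = 10 of 5 × 3 = 15.
- Through Cycle 26 (25 cycles): 25 × 2 = 50 of 25 × 3 = 75. This is a ceiling.

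The ratio is the same throughout. The totals only show how often the gap recurs.

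**Who is exposed.** A day 15 count below 500/µL for ANC or below 50,000/µL for platelets is Grade 4 neutropenia or at least Grade 3 thrombocytopenia (Section 5.5.2). It therefore starts twice-weekly checks, which would reach day 22. The day 22 gap thus concerns patients whose day 15 count was acceptable. The day 8 gap concerns every patient who enters the cycle with no trigger in force.

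**Day label.** The 48-hour window before day 21 is days 19 to 21; before day 22 it is days 20 to 22. A count on day 19 satisfies the label in Section 5.2.1 but is 22 − 19 = 3 days old at the day 22 dose.

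**The case against.** The strongest reply is that nothing forbids the missing counts. Section 5.2.1 demands them, the schedule lists routine draws, and a site can satisfy both by drawing the CBC. The Cycle 2+ map refers readers to Sections 5.2 and 5.0, and footnote 1 on the CBC row of Section 8.1 points to Section 5.2.1. Other safeguards bound the risk: full eligibility counts before every cycle, weekly counts in Cycle 1, the day 15 count, and closer checks once toxicity is known.

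Much of this stands. A site that reads Section 5.2.1 closely will draw the counts, and harm arises only where a site does not. The safeguards are real. The day 21 label is a separate slip and adds nothing to the CBC gap.

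It does not remove the conflict. Item e and footnote 6 order weekly CBCs as a special requirement for dose-adjusted patients, which implies that other patients are not on weekly counts. The summary of changes, taken only as context, records that weekly CBCs in Cycles 2+ were removed on purpose. The footnote 1 pointer follows a sentence about hematologic DLT and can be read as confined to it, while item e and footnote 6 send the reader to Section 6.1. The heading of Section 5.2.1 speaks of recommendations, but its text is mandatory.

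**Conclusion.** The concern holds. In each cycle from Cycle 2 onward, 2 of the 3 within-cycle checks that Section 5.2.1 requires have no routine CBC behind them. The latest scheduled count is 7 to 10 days old at day 8 and 7 days old at day 22, against a 2-day limit. Section 5.2.1 also disagrees with the treatment plan and both delivery maps on the start of the fourth block (day 21 against day 22).

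This rests on two readings: that Section 5.2.1 applies in every cycle, as its wording indicates, and that the patient has no trigger for additional CBCs. The number of holds that would be missed cannot be estimated, because the documents give no rate of new cytopenia after Cycle 1. The dose-escalation DLT period and the MTD/RP2D decision are not affected, and no effect on the response endpoint has been shown. Because the gap sits in a safety hold rule, the text should be corrected.

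**What to change.** Reconcile Sections 5.2.1, 5.5.2, 5.7 item e and 8.1 (footnotes 1 and 6) so that, in Cycles 2+, the blocks subject to the count rule and the days on which a CBC is scheduled are the same. Make the Cycle 2+ map match. Give the fourth block the same start day in Section 5.2.1 and in the dosing tables. The 72-hour window before a cycle and the 48-hour window within a cycle govern different events and need not be merged. Which passage governs is for the clinical team; this review takes no position.

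The cost is a protocol wording amendment. Depending on which passage is kept, it brings either no new tests or two more routine CBCs per cycle in the Cycle 2+ schedule. Sites that already follow Section 5.2.1 to the letter would be drawing those two counts now.

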6.1 Dose Modifications for Hematological Toxicity

- 6.1.1 Patients who have dose-limiting thrombocytopenia or neutropenia (defined in [section 5.2](#), [section 5.2.1](#) and [section 5.5.2](#)) should receive subsequent cycles with at least a 25% dose reduction (75% of the original dose). Please see dosing nomograms in [Appendix V](#). For patients ≥ 18 years of age with starting dose of 40 mg BID, dose should be reduced to 30 mg BID 3 days on, 4 days off per week (25% dose reduction).
- 6.1.2 Patients who experience dose-limiting thrombocytopenia and/or neutropenia (as defined [in Section 5.5.2](#)) after one dose reductions must be removed from protocol therapy.
- 6.1.3 Patients who have a dose-limiting hematological toxicity that does not resolve to eligibility parameters within 14 days after the planned start of the next treatment cycle (42 days from start of previous cycle) must be removed from protocol therapy.

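### Section 5.2.1 twice gives day 21 as the start of the fourth weekly dosing block; every dosing schedule in the protocol gives day 22

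*Combined protocol and SAP*

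**What the plan says.** Section 5.2.1 describes the drug as "administered on a 3-day on and 4-day off schedule, repeated 4 times each cycle". It requires minimum neutrophil and platelet counts "within 48 hours prior to initiation of each 3 day interval", and a parenthesis then spells out the days: "ANC and platelet parameters must be met (without transfusion) within 48 hours of initiation of days 8, 15, and 21". If the counts are not met, the block is omitted and dosing is "attempted to restart the following week (e.g. day 15 or 21".

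The other places that give the schedule are:

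- **Section 5.1 table:** the week 4 doses are on days 22 to 24. Days 18 to 21 form a row with no drug.
- **Section 5.6, Cycle 1 delivery map:** dosing days "1-3 8-10 15-17 22-24". The day 21 row has no dose line, and a CBC is listed on day 22.
- **Section 5.7, Cycles 2+ delivery map:** the same dosing days, again with no dose line on day 21.
- **Appendix VI diary:** the week 4 entries are for days 22, 23 and 24.

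Two other rules refer to Section 5.2.1. One is the hematological DLT criterion in Section 5.5.2 that begins "Failure to meet hematological criteria to initiate weekly dosing". The other is the dose-reduction rule in Section 6.1.1 that begins "Patients who have dose-limiting thrombocytopenia or neutropenia".

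**The concern.** The day list is there to tell sites which calendar days the count check applies to, and one of its three days is not a dosing day. The restart sentence repeats the same wrong day, so a single slip in one list does not explain it.

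What is at stake is the timing of a safety check for a drug whose commonest toxicities, according to Section 5.2.1, are hematologic. A site that works from the list could time the fourth-block count, or the restart, one day early.

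The exposure differs by cycle. In Cycle 1 the delivery map independently places a CBC on day 22. In Cycles 2+, the routine CBCs in Section 5.7 and in the Section 8.1 footnote fall within 72 hours of cycle start and on day 15. Weekly CBCs apply only after a dose adjustment for hematologic toxicity, and more frequent checks only for severe cytopenia or DLT. For other patients in Cycles 2+, Section 5.2.1 is the only text that names a day for the fourth-block check.

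**Working it through.** **Inputs.** A 3-day-on, 4-day-off pattern, so a period of 3 + 4 = 7 days, given four times per cycle (Section 5.2.1). The cycle lasts 28 days (Section 5.1). The days listed in Section 5.2.1 are 8, 15 and 21.

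**1. Block start days.** Block k starts on day 1 + 7(k − 1):

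| Block | Formula | Start day | Section 5.2.1 | Section 5.1, both maps, diary |
|---|---|---|---|---|
| 1 | 1 + 7×0 | 1 | not listed | 1 |
| 2 | 1 + 7×1 | 8 | 8 | 8 |
| 3 | 1 + 7×2 | 15 | 15 | 15 |
| 4 | 1 + 7×3 | 22 | **21** | 22 |

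Days 8 and 15 reproduce. Day 21 does not; the error is 22 − 21 = 1 day.

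**2. Spacing of the listed days.** 15 − 8 = 7 days, but 21 − 15 = 6 days. With day 22 the second gap is 22 − 15 = 7 days.

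**3. Off-drug days.** If block 3 is given on days 15 to 17, a start on day 21 leaves days 18, 19 and 20 off drug: three days, not four. A start on day 22 leaves days 18 to 21: four days.

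**4. Restart rule.** A block omitted on day 8 and tried again one week later restarts on day 8 + 7 = 15, which matches the text. A block omitted on day 15 restarts on day 15 + 7 = 22, not 21.

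**5. Count window.** Forty-eight hours before day 21 reaches back to day 19. From day 19 to the actual dose on day 22 is (22 − 19) × 24 = 72 hours, against the intended 48.

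**6. What does not change.** With either start day there are 4 blocks × 3 days = 12 dosing days, or 12 × 2 = 24 administrations, per cycle. The 75% rule in Section 5.5.2 (9 of 12, so expressed in dosing days) is unaffected.

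**The case against.** The strongest reply is that the protocol corrects itself. The binding requirement is the general clause, which ties the check to the start of each 3-day interval. The day list only illustrates it, and the restart day is given only as an example. The restart sentence also speaks of the following week, which after day 15 can only mean day 22. No map or diary has a dose line for day 21, so a site that follows the forms will dose correctly. A count on day 20 or 21 will usually satisfy both readings; only an earlier one, around day 19, separates them, and the general clause rules that one out. Section 8.0 also tolerates minor unavoidable departures of up to 72 hours.

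Most of this stands, and it is why the point is minor. It does not make the text right. The list claims to state what the general clause means and misstates it, and the restart error is in a separate sentence. The Section 8.0 tolerance covers logistical departures, not a wrong day in the rule.

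Two further objections also stand:

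- The rules in Sections 5.5.2 and 6.1.1 that cite Section 5.2.1 do not use the day list. The citations show that the section is operative, not that any DLT would be misclassified.
- Correcting the day does not by itself reconcile Section 5.2.1, which asks for counts before every block, with the Cycles 2+ schedule, which has no routine CBC at block 4.

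**Conclusion.** The inconsistency is real. Section 5.2.1 gives the fourth block's start day as 21 in two places. Four schedule sources and the section's own weekly pattern give 22.

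The error is one day in each place. Its worst literal consequences are a count up to about 72 hours old at the day 22 dose, or a fourth block started after three off-days. Dosing on day 21 is unlikely given the forms. There is no effect on doses per cycle, the 75% rule, DLT classification, sample size or error rates.

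The conclusion assumes only that the 3-on/4-off weekly schedule is the intended one, which every schedule source supports. The text concerned is current protocol text, not an amendment log. Severity: minor.

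**What to change.** In Section 5.2.1, replace 21 with 22 in both places, so that the count-check days read 8, 15 and 22 and the restart example reads day 15 or 22. Nothing else in the section needs to change for this point. The cost is two numbers at the next amendment, with no new procedures, visits, patients or dosing restrictions.
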